#### 8.1.2 Secondary study parameters/endpoints

- Stent-related complications according to Clavien-Dindo grading system within 90 days (see Table 2.).
- Absolute and relative (%) bilirubin decrease after 14 days.
- Number of scheduled and unscheduled reinterventions within 90 days.
- Infectious biliary complications (i.e. cholangitis and cholecystitis);
- Technical success of stent placement at initial drainage procedure;
- Bile culture results;
- QoL, measured with the EORTC Quality of Life Questionnaire C-30 (QLQ-C30) and its biliary cancer module (QLQ-BIL21) (see Appendix C and D);
- Proportion of patients that became eligible for palliative chemotherapy, based on bilirubin level below 20 mmol/l and good performance status (ECOG < 2);
- Cost-effectiveness.

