#### **Quality of life**

Patients complete questionnaires (QLQC30/BIL21) (see Appendix C and D) at the day of informed consent, and at 14 days, 28 days, and 90 days after the first intervention.

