### 10.2 Secondary study parameter(s)

Pilot cohort and overall analysis

The secondary outcomes for safety and feasibility are the stent-related complications, the amount of reinterventions in 90 days, absolute and relative (%) decrease of bilirubin in 14 days, infectious biliary complications (i.e. cholangitis and cholecystitis), technical success of stent placement at initial drainage procedure, proportion of patients that started with palliative chemotherapy and cost-effectiveness. The proportion and 95% confidence interval will be calculated for the continuous variables. The median and interquartile range will be measured for the numeric variables.

Expansion cohort

QoL is measured with (QLQC30/BIL21) (see Appendix C and D). Repeated measurement analysis will be used to evaluate within group differences. the repeated measurements will be analyzed separately using linear mixed models with correction for the baseline score (added as covariate). The single items in the QLQ-C30 will be analyzed using (ordinal) logistic regression with random effects. The BIL21 questionnaire will also be used as utility measure for the cost-effectiveness analysis.

We will perform a cost-effectiveness analysis to evaluate the impact of percutaneous placement of metal stents in patients with unresectable pCCA. The cost-effectiveness analysis from the healthcare sector perspective will consider direct medical costs of both strategies. Prospective patient-level cost data collection for each patient in the trial would be ideal but is too expensive to collect. Instead, we will model costs in a decision model using probabilities of events and unit costs of interventions.

Data from a comparable matched cohort of both participating centers of patients treated with endoscopic drainage in the period before the current trial, will be used as a comparison. The health effects will be expressed in quality-adjusted life years (QALYs). The QALY combines the number of life years with the quality of life measured with the EQ-5D utilities. The cost-effectiveness of percutaneous placement of metal stents will be expressed as the incremental costs per QALY gained to allow comparison with other (unrelated) health care

---

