**EORTC QLQ – BIL21**

Soms zeggen patiënten dat ze volgende klachten of problemen hebben. Wilt u aangeven in welke mate u deze symptomen of problemen gedurende de afgelopen week heeft ervaren? Wilt u uw antwoord geven door het cijfer te omcirkelen dat het meest op u van toepassing is?

Gedurende de afgelopen week:		Helemaal niet	Een beetje	Nogal	Heel erg
31.	Heeft u problemen met eten gehad?	1	2	3	4
32.	Heeft u het gevoel gehad te snel voldaan te zijn nadat u bent begonnen te eten?	1	2	3	4
33.	Heeft u problemen gehad met uw smaakzin?	1	2	3	4
34.	Bent u beperkt geweest in het soort voedsel dat u kon eten ten gevolge van uw ziekte of behandeling?	1	2	3	4
35.	Zijn uw huid of ogen geel (geelzucht) geweest?	1	2	3	4
36.	Heeft u jeuk gehad?	1	2	3	4
37.	Heeft u zich zorgen gemaakt omdat uw huid geel was?	1	2	3	4
38.	Bent u minder actief geweest dan u had willen zijn?	1	2	3	4
39.	Heeft u zich 'futloos' gevoeld?	1	2	3	4
40.	Heeft u een tekort aan energie gehad?	1	2	3	4
41.	Heeft u 's nachts pijn gehad?	1	2	3	4
42.	Heeft u pijn gehad in de maagstreek?	1	2	3	4
43.	Heeft u pijn in uw rug gehad?	1	2	3	4
44.	Heeft u een opgeblazen gevoel in uw buik gehad?	1	2	3	4
45.	Heeft u zich gestrest gevoeld?	1	2	3	4
46.	Heeft u het minder makkelijk gevonden om u te amuseren?	1	2	3	4
47.	Heeft u zich zorgen gemaakt over uw toekomstige gezondheidstoestand?	1	2	3	4
48.	Heeft u zich zorgen gemaakt over uw familie in de toekomst?	1	2	3	4
49.	In hoeverre heeft u last gehad van bijwerkingen van uw behandeling?	1	2	3	4
50.	Heeft u problemen gehad met drainage slangen/opvangzakken?	1	2	3	4
51.	Heeft u zich zorgen gemaakt over gewichtsverlies?	1	2	3	4

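### Section 10.2 names two conflicting utility sources for the QALY, one never scheduled and one without preference weights, so the cost per QALY cannot be computed from what the protocol specifies

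*Protocol*

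**What the plan says.** Cost-effectiveness is a secondary objective (section 2) and a secondary endpoint (section 8.1.2). Section 10.2 fixes its form: "The cost-effectiveness of percutaneous placement of metal stents will be expressed as the incremental costs per QALY gained".

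For the utility that turns life years into QALYs, section 10.2 makes two statements:

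- In the paragraph on quality of life: "The BIL21 questionnaire will also be used as utility measure for the cost-effectiveness analysis".
- In the paragraph on the economic analysis: "The QALY combines the number of life years with the quality of life measured with the EQ-5D utilities".

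What patients are asked to complete is set elsewhere. The endpoint in section 8.1.2 reads "QoL, measured with the EORTC Quality of Life Questionnaire C-30 (QLQ-C30) and its biliary cancer module (QLQ-BIL21) (see Appendix C and D", and the schedule in section 8.3 reads "Patients complete questionnaires (QLQC30/BIL21) (see Appendix C and D) at the day of informed consent, and at 14 days, 28 days, and 90 days", counted from the first intervention. Neither mentions EQ-5D.

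Section 10.2 describes a decision model that takes costs from event probabilities and unit prices. The comparator is a matched cohort treated endoscopically before the trial. Probabilistic sensitivity analysis, acceptability curves and value-of-information analysis are to follow.

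**The concern.** A QALY needs a preference-based weight for time spent in each health state. Section 10.2 names two instruments for that weight without linking or ranking them, and neither works as the protocol stands. EQ-5D is said to measure quality of life but is never scheduled. The BIL21 is scheduled but comes with no rule for turning its answers into a utility.

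An analyst following the text would have to choose between an empty data field and a symptom-and-concern score relabelled as a utility. The second is the worse outcome, because it would yield a plausible-looking cost per QALY without a valid denominator. The sensitivity, acceptability and value-of-information analyses would all inherit that input.

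**Working it through.** The plan states no figure to reproduce. The check is whether each input to the planned result has a stated source.

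**1. What the result requires.** With P for percutaneous stenting and E for endoscopic drainage:

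cost per QALY gained = (cost_P − cost_E) / (QALY_P − QALY_E)

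QALY = sum over health states of (time in state × utility of state)

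**2. Where each input comes from.**

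- Costs: event probabilities and unit prices in the decision model (section 10.2). A source is stated.
- Time: survival and vital status are collected in the trial (sections 8.1.1 and 8.3), and section 10.2 names the matched cohort as comparator. A source is stated in outline.
- Utility: EQ-5D in one sentence and BIL21 in another (section 10.2).

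**3. Is EQ-5D collected?** The protocol schedules questionnaires at four moments: consent and days 14, 28 and 90. At each of them the instruments are the QLQ-C30 and BIL21. EQ-5D is due at 0 of 4. The sentence in section 10.2 is the only place where the protocol mentions it. I do not rely on its absence from the appendices, because the available text of Appendix C breaks off after item 14.

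**4. Can the BIL21, as specified, stand in?** Appendix D introduces it with "Soms zeggen patiënten dat ze volgende klachten of problemen hebben" (roughly, patients sometimes report the following complaints or problems). Its items run from 31 to 51, which is 51 − 31 + 1 = 21 items, each answered 1 (not at all) to 4 (very much). A raw sum would run from 21 × 1 = 21 to 21 × 4 = 84, with higher values meaning more trouble. Rescaling that range to 0–1 would not make it a utility: its lower end would be the worst set of answers rather than death, and all items would count equally rather than by preference. The protocol gives no value set, weights or mapping that would do the conversion.

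**5. Is another source stated?** Section 10.2 mentions no mapping from the QLQ-C30 and no external set of health-state utilities. The decision model is described only as the means of obtaining costs.

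**6. Timing.** Section 3 reports 30 patients included by July 2022, out of 67 planned. From that date, direct EQ-5D data could cover at most 67 − 30 = 37 patients (37/67 = 55%), and fewer with each later inclusion. The document does not show whether accrual is still open.

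**The case against.** The strongest reply is that this is a model-based evaluation. A decision model can take utilities by health state from published EQ-5D values or from a mapping, and a statistical or health-economic plan may properly hold that detail. This stands in part. A reader might infer that cost per QALY cannot be obtained at all, and the documents do not support that: the QLQ-C30 is scheduled and could be mapped, and external utilities could be used. What remains is that the protocol states neither route, that its two sentences on the utility source conflict, and that no later plan can supply EQ-5D responses that were never scheduled.

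Four further readings go beyond the text:

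- *The 10 pilot patients (10/67 = 15%) have no quality-of-life plan.* Sections 2 and 10.2 place quality of life under the expansion cohort, but sections 8.1.2 and 8.3 carry no such restriction. The protocol is ambiguous here, not silent.
- *The comparator cohort has no utilities.* Section 10.2 does not say what data that cohort holds, so a count of zero would be inferred from silence. A model with health-state utilities does not need questionnaires from those patients.
- *Questionnaires stop at day 90, so later survival cannot be valued.* Extrapolation is ordinary modelling detail and not a separate error.
- *The BIL21 can never yield a utility.* Whether weights or a mapping exist outside the protocol cannot be settled from it. The supportable statement is that the protocol gives none.

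**Conclusion.** The point holds in this form: section 10.2 names two conflicting utility sources, EQ-5D is due at 0 of the 4 questionnaire moments, and the BIL21 comes without preference weights. The cost per QALY therefore cannot be computed from the data and methods that the protocol specifies.

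This rests on the text of sections 8.1.2, 8.3 and 10.2 and on the BIL21 as printed in Appendix D. It assumes that no other approved document already adds EQ-5D to the visits or names a mapping. If one does, what remains is to correct section 10.2.

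It should be fixed, but it does not threaten the trial. Cost-effectiveness is one of several secondary endpoints in a single-arm study. The primary overall survival analysis, the sample size and the safety outcomes do not depend on it.

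**What to change.** - Delete the sentence in section 10.2 that makes the BIL21 a utility measure, and keep the BIL21 as a quality-of-life outcome.
- Name one utility source and apply it by health state to both strategies in the decision model. It can be a pre-stated mapping from the scheduled QLQ-C30 to EQ-5D utilities, or a stated external EQ-5D utility set. Working by health state also means that not every patient, and no historical patient, needs a questionnaire.
- If accrual is still open, add EQ-5D to section 8.1.2 and to the four existing moments in section 8.3 for the remaining patients. Use one source throughout as the base case and the other as a sensitivity analysis. Do not pool mapped values from early patients with direct values from later ones: the first 30 appear to come from Erasmus MC, while the second expansion adds six centres performing their first 5 cases each, so instrument would be mixed with centre, period and learning curve.
- State whether the quality-of-life questionnaires apply to the pilot patients, since that decides how many QLQ-C30 forms there are to map.

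The cost is a small amendment, some mapping uncertainty that the planned probabilistic sensitivity analysis can carry, and, if EQ-5D is added, one short extra questionnaire for palliative patients at existing questionnaire moments. Naming a mapping or an external set alone resolves the contradiction without that extra burden.

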### **10.3 Other study parameters**

Not applicable.

### **10.4 Interim analysis (if applicable)**

Interim analyses will not be performed during this pilot study.

## 11. ETHICAL CONSIDERATIONS

### 11.1 Regulation statement

The investigator will ensure that this study is conducted to the standards of Good Clinical Practice, in full conformance with the "Declaration of Helsinki" (64yh World Medical Association General Assembly, latest amendment Fortaleza, Brazil, October 2013), the Dutch laws and regulations with the WMO ("Wet Medisch-wetenschappelijk Onderzoek met mensen") in particular.

### 11.2 Recruitment and consent

Patients will be asked to participate in this study when they are seen at the outpatient clinic. Initially, the patient will be informed of the nature of the study and will be given pertinent information as to the intended purpose of the study by the treating physician or study coordinator. The procedures and possible hazards to which the patient will be exposed will be explained. The patient will also receive written information (patient information form). After receiving study information, patients will be given enough time to consider whether they wish to participate or not. Prior to the screening evaluation, an informed consent statement, as approved by the Medical Ethical Committee Erasmus MC Rotterdam will be read and signed by the patient, and the responsible physician/coordinating investigator. The patient will be provided with a second original form of the signed informed consent statement. The patient may withdraw from the study at any time.

The investigator shall provide a copy of the information sheet and the signed consent form to the patient and the signed original shall be maintained in the Investigator Site File.

### 11.3 Objection by minors or incapacitated subjects (if applicable)

Not applicable, as no minors or incapacitated subjects are eligible for this study.

### 11.4 Benefits and risks assessment, group relatedness

For eligible patients, curative surgical treatment is not possible and the median survival time is short. Palliative treatment is aimed at obtaining adequate biliary drainage followed by palliative systemic chemotherapy.

90-day mortality with the current standard of care of endoscopic drainage was 35%. The percutaneous intervention is an alternative approach. We hypothesize that direct percutaneous SEMS placement in patients with unresectable pCCA reduces post-drainage cholangitis and mortality, requires fewer reinterventions, and increases the rate of patients receiving palliative chemotherapy. Specific complications related to the percutaneous approach are bleeding and bile leakage, which are uncommon (<5%).

In this study, patients will undergo an invasive procedure with hospital discharge after a few days. This corresponds to the standard of care. Follow-up appointments are planned 14 days (T1), one month (T2) and three months (T3) after stent placement. These visits will take 30 minutes. T2 and T3 are extra visits compared to standard of care.

### **11.5 Compensation for injury**

The sponsor/investigator has a liability insurance which is in accordance with article 7 of the WMO.

The sponsor (also) has an insurance which is in accordance with the legal requirements in the Netherlands (Article 7 WMO). This insurance provides cover for damage to research subjects through injury or death caused by the study.

The insurance applies to the damage that becomes apparent during the study or within 4 years after the end of the study.

### **11.6 Incentives (if applicable)**

Not applicable, as there is no subsidising party for this study.

## 12. ADMINISTRATIVE ASPECTS, MONITORING AND PUBLICATION

### 12.1 Handling and storage of data and documents

#### **Patient confidentiality**

Each patient is assigned a unique patient study number at enrolment, which is used to code ( 001, 002 etc.) the patient's identity in the study documents.

The investigator will keep a subject enrolment and identification log that contains the key to the code, i.e. a record of the personal identification data linked to each patient study number. This record is filed at the investigational site and should only be accessed by the investigator and the supporting site staff, and by representatives of the Sponsor or a regulatory agency for the purpose of monitoring visits or audits and inspections.

#### **Case Report Forms**

Data will be collected on electronic Case Report Forms (CRF) in OpenClinica to document eligibility, safety and efficacy parameters, compliance to treatment schedules and parameters necessary to evaluate the study endpoints. Data to be collected on the e-CRF are derived from the protocol.

#### **Filing of essential documents**

Essential Documents are those documents that permit evaluation of the conduct of a trial and the quality of the data produced. The essential documents may be subject to, and should be available for, audit by the Sponsor's auditor and inspection by the regulatory authority(/-ies).

The investigator should file all essential documents relevant to the conduct of the study on site in the Investigator Site File. The Sponsor will file all essential documents relevant to the overall conduct of the trial in the Trial Master File. Essential documents should be filed in such a manner that they are protected from accidental loss and can be easily retrieved for review.

#### **Record retention**

Essential documents should be retained for 15 years after the end of the study (i.e. from date of last patient visit for this study). They should be destroyed after this time.

Source documents (i.e. medical records) of patients should be retained for at least 15 years after the end of the study. Record retention and destruction after this time is subject to the site's guidelines regarding medical records.

## **12.2 Monitoring and Quality Assurance**

Based on the guideline by the NFU (Dutch Federation of University Medical Centers) about quality insurance in human research (“Kwaliteitsborging van mensgebonden onderzoek”) we qualify the risk of this study as ‘low’.

On behalf of the Sponsor the monitor will perform on-site monitoring visits to verify that the rights and well-being of patients are protected, the reported trial data are accurate, complete, and verifiable from source documents and the conduct of the trial is in compliance with the currently approved protocol/amendments(s), with GCP, and with the applicable regulatory requirement(s). Our sourcedata is the electronical health record at Erasmus MC (HiX). If patients returned to their referring hospital or if visits are too stressfull, the T2 and T3 visits will be telephone calls.

A monitor will be appointed prior to the start of the study. The monitor will evaluate at least the safety and outcome parameters at regular intervals, in compliance with the risk class assessment (see monitoring plan and associated risk class A/B/C appendix).

## **12.3 Amendments**

Amendments are changes made to the research after a favourable opinion by the accredited METC has been given. All amendments will be notified to the METC that gave a favourable opinion.

## **12.4 Annual progress report**

The sponsor/investigator will submit a summary of the progress of the trial to the accredited METC once a year. Information will be provided on the date of inclusion of the first subject, numbers of subjects included and numbers of subjects that have completed the trial, serious adverse events/ serious adverse reactions, other problems, and amendments.

## **12.5 Temporary halt and (prematurely) end of study report**

The investigator/sponsor will notify the accredited METC of the end of the study within a period of 8 weeks. The end of the study is defined as the last patient’s last visit.

The sponsor will notify the METC immediately of a temporary halt of the study, including the reason of such an action.

In case the study is ended prematurely, the sponsor will notify the accredited METC within 15 days, including the reasons for the premature termination.

Within one year after the end of the study, the investigator/sponsor will submit a final study

---

report with the results of the study, including any publications/abstracts of the study, to the accredited METC.

### **12.6 Public disclosure and publication policy**

Publications resulting from this study will be submitted to peer-reviewed journals. The projectleader and co-investigators will prepare the manuscript together with those who substantially contributed to the study. Specification for authorship have been summarized in the appendix (appendix B). Any publication, abstract or preservation based on patients included in this study must be approved by the projectleader and the co-investigators. This is applicable to any individual patient registered in the trial, or any subgroup of the trial patients. Such a publication cannot include any comparisons between randomized treatment arms or an analysis of any of the study end-points unless the final results of the trial have already been published. Information about this study is also included in an online overview of medical research studies, [www.trialregister.nl](http://www.trialregister.nl).

### **13. STRUCTURED RISK ANALYSIS**

#### **13.1 Potential issues of concern**

Skipped.

#### **13.2 Synthesis**

Section 13.1 is skipped, because the intervention will be done with a registered product which is to be used within the indication. The risks of transhepatic biliary drainage include cholangitis (8%), pancreatitis (3%), bleeding which is limited to liver and bile ducts or bleeding in the abdominal cavity (2%), and leak of the bile into the abdominal cavity or into the space around the lung (<1%) (15). With a percutaneous approach without crossing the ampulla the risk of post-drainage cholangitis and mortality is expected to be reduced

**APPENDICES****Appendix A: Product characteristics SEMS**

At Erasmus MC two different uncovered stents are used to prevent there are no stents available if there is a short of stock at one of the manufacturers. There are no differences in length or diameter.

*The product characteristics of the ' HILZO Biliary Uncovered Stent, BCM ' is available via the link displayed below on page 5.*

[https://www.kebomed.nl/files/169/hilzo\\_stents\\_catalogue.pdf](https://www.kebomed.nl/files/169/hilzo_stents_catalogue.pdf)

*The product characteristics of the 'WALLSTENT-UNI™ Endoprosthesis Self-Expanding Stent' is available via the link displayed below.*

[http://genodynamic.ro/wp-content/uploads/2015/03/DINPER2042EF\\_Wallstent\\_Brochure\\_English.pdf](http://genodynamic.ro/wp-content/uploads/2015/03/DINPER2042EF_Wallstent_Brochure_English.pdf)

